1. INTRODUCTION

This document describes the rules and conventions to be used in the presentation and analysis of efficacy and safety as described in Section 9 of the study protocol. It describes the data to be summarized and analyzed, including specifics of the statistical analyses to be performed. This statistical analysis plan (SAP) is based on protocol version 5.0, dated 22nd July 2019.

2. STUDY OBJECTIVES

2.1. Primary Objective

To investigate the bronchodilator effect of different doses of RPL554 administered by nebulizer on change from baseline in peak forced expiratory volume in 1 second (FEV₁) (maximum over 3 hours following dosing) at the final study visit (i.e., Week 4) when administered twice daily to patients with moderate to severe chronic obstructive pulmonary disease (COPD) on a background of once-daily tiotropium.

2.2. Secondary Objective

- To investigate the bronchodilator effect of RPL554 administered by nebulizer on average area under the curve AUC_{0-3h} FEV₁ at Week 4
- To investigate the bronchodilator effect of RPL554 administered by nebulizer on average AUC_{0-12h} FEV₁ at Week 4
- To investigate the effect of RPL554 administered by nebulizer on change from baseline in morning trough FEV₁ at Week 4
- To investigate the effects of RPL554 on COPD symptoms, as measured by daily diary (Evaluating Respiratory Symptoms for COPD [E-RSTM:COPD], St. George's Respiratory Questionnaire [SGRQ-C], Baseline Dyspnea Index [BDI]/Transition Dyspnea Index [TDI] and patient global assessment of change [PGAC])
- To investigate the bronchodilator effect of RPL554 administered by nebulizer on peak FEV₁, trough FEV₁ and average AUC_{0-3h} FEV₁ at Weeks 1, 2 and 3
- To investigate the bronchodilator effect of RPL554 administered by nebulizer on peak FEV₁, average AUC_{0-3h} FEV₁ and average AUC_{0-12h} FEV₁ at Day 1
- To investigate the safety of RPL554 when administered for 4 weeks in patients with COPD, as measured by adverse events (AEs), laboratory tests, 12-lead electrocardiograms (ECGs) and vital signs
- To investigate the effect of RPL554 on rescue albuterol use
- To investigate the bronchodilator effect of RPL554 administered by nebulizer on peak and average AUC_{0-3h} forced vital capacity (FVC) on Day 1 and at Weeks 1 to 4, in average AUC₀₋₁₂ FVC on Day 1 and at Week 4 and in morning trough FVC at Weeks 1 to 4.

Document: ...\\Verona_Pharma\\RPL554\\BZA48916\\Biostatistics\\Documentation\\SAP\\Verona CO-205 SAP v1.0

Author: [REDACTED]

Version Number: V1.0

Version Date: 05DEC2019

Template No.: CS_TP_BS016 Revision 5

Reference: CS_WI_BS005

Effective Date: 01Apr2018

- To evaluate the steady state exposure of RPL554
- To evaluate the effect of RPL554 on tiotropium steady state exposure

2.3. Exploratory Objective

[figure not shown]
- To assess the change from baseline FEV₁ to peak and average AUC_{0-12h} FEV₁ at Week 4 compared to Day 1
- To investigate the effect of RPL554 on inspiratory capacity (IC) on Day 1 and at Week 4
- To investigate the effects of RPL554 on COPD symptoms, as measured by the COPD Assessment Test (CAT)
- To assess the effect of RPL554 on morning symptoms and activity limitation

3. STUDY DESIGN

3.1. General Description

This is a Phase IIb, randomized, double-blind, placebo-controlled dose ranging, parallel group study. A flow chart illustrating the key components of the study is provided in Figure 1.

Figure 1: Study Flow Chart

Document: ...\\Verona_Pharma\\RPL554\\BZA48916\\Biostatistics\\Documentation\\SAP\\Verona CO-205 SAP v1.0

Author: [REDACTED] Version Number: V1.0

Version Date: 05DEC2019

Template No.: CS_TP_BS016 Revision 5

Reference: CS_WI_BS005

Effective Date: 01Apr2018

At the pre-screen visit patient will be asked to sign the informed consent, will receive their patient identification number and commence washout of prohibited medications. Patients will be dispensed rescue medication to be used as needed for increased pulmonary symptoms during the screening run-in and treatment periods.

After patients provide informed consent and following at least a 48-hour washout of all long-acting bronchodilators, they will be screened for eligibility including a reversibility test (spirometry both pre- and post-four puffs of albuterol). Eligible patients will enter a 14-day run-in and be dispensed open-label tiotropium (Spiriva® Respimat) and an electronic diary (e-diary) for recording symptoms, assessing rescue usage and confirming twice daily dosing with study treatment. Starting the day after Screening (Visit 1) patients will start taking open-label tiotropium (Spiriva® Respimat®) once daily in the morning.

At Day 1 patients will be re-assessed for eligibility according to the Randomization Criteria, which can be found in Section 4.3 of the study protocol. Eligible patients will be stratified based on the reversibility to albuterol, as determined at Screening (“reversible”, “non-reversible”), then randomized to one of the five treatment groups within each reversibility stratum. After randomization, patients will take their tiotropium dose 2 minutes prior to their first dose of double-blind study treatment (RPL554 or placebo). Patients will remain in the clinic for 12 hours to undergo serial spirometry and other assessments. They will then take their second dose of study treatment in the evening prior to clinic discharge. Patients will return to the clinic for 3 weekly visits. In between visits, patients will take the study treatment twice a day (morning and evening) and tiotropium once a day in the morning, in the same order as described above.

Patients will be instructed to withhold study treatment, tiotropium and rescue medication prior to study visits. Rescue medication will need to be withhold prior to the visit for at least 6 hours.

Approximately 400 patients with COPD aged 40 to 80 years (inclusive) will be randomized equally to receive RPL554 (four possible doses) or placebo (Figure 1). Study treatment will be administered double-blind to minimize any potential bias in the overall assessment of treatment effect and safety.

3.2. Schedule of Events

Schedule of events can be found in Section 6.0 of the study protocol.

3.3. Changes to Analysis from Protocol

No changes to the analysis outlines in the protocol are planned.

Document: ...\\Verona_Pharma\\RPL554\\BZA48916\\Biostatistics\\Documentation\\SAP\\Verona CO-205 SAP v1.0

Author: [REDACTED] Version Number: V1.0

Version Date: 05DEC2019

Template No.: CS_TP_BS016 Revision 5

Reference: CS_WI_BS005

Effective Date: 01Apr2018

4. PLANNED ANALYSES

A final analysis after database lock is planned for this study.

4.1. Data Monitoring Committee (DMC)

There will be no data monitoring committee (DMC) for this study.

4.2. Interim Analysis

There will be no formal, unblinded interim analysis for this study. To assess the plausibility of the assumptions in the sample size calculation, peak FEV₁, trough FEV₁, AUC₀₋₃ FEV₁ and AUC_{0-12h} FEV₁ will be calculated on blinded data after completion of 125 patients. If the estimated standard deviation has an increase of 12% or less, then there will be no revised sample size made. However, if the estimated standard deviation has an increase of 20% or more, a revised sample size estimation using the new standard deviation and the previously assumed difference of 93 mL will be performed. If the increase in estimated standard deviation will be between 12% and 20% then a decision to review the sample size will be taken based on further examination of the data.

4.3. Final Analysis

All final, planned analyses identified in this SAP will be performed by IQVIA Biostatistics following sponsor authorization of this SAP (and associated output shells), database lock, analysis sets and unblinding of treatment.

5. ANALYSIS SETS

Agreement and authorization of patients included/ excluded from each analysis set will be conducted prior to the unblinding of the study.

Analyses will be performed for the population sets described in Table 1.

Table 1: Use of the analysis set

	All Patients Enrolled Set	All Patients Randomized Set	Full Analysis Set	Per-Protocol Analysis Set	Safety Analysis Set	PK data Set
Disposition of patients	X					
Protocol deviations	X					
Demographic and other baseline characteristics		X				
Medical history		X				
Prior and concomitant medication		X			X	
Treatment compliance and extent of exposure					X	
Efficacy: Primary endpoint			X	X		
Efficacy: Secondary endpoints			X	X		
Efficacy: Exploratory endpoints			X			
Sensitivity Analyses (incl. primary and selected secondary endpoints) *			X			
Safety					X	
Pharmacokinetic						X

* ANCOVA analyses of the primary endpoint (change from baseline FEV₁ to peak FEV₁ at Week 4), and key secondary endpoints (change from baseline FEV₁ to average AUC_{0-12h} FEV₁ at Week 4 and change from baseline in total E-RS™:COPD score at Week 4).

5.1. All Patients Enrolled Set [ENR]

The all patients enrolled (ENR) set will contain all patients who provide informed consent for this study. Depending on the data that is being analysed, patients will either be classified according to randomized treatment or actual treatment received, specified in the relevant section.

Document: ...\\Verona_Pharma\\RPL554\\BZA48916\\Biostatistics\\Documentation\\SAP\\Verona CO-205 SAP v1.0

Author: [REDACTED] Version Number: V1.0

Version Date: 05DEC2019

Template No.: CS_TP_BS016 Revision 5

Reference: CS_WI_BS005

Effective Date: 01Apr2018

5.2. All Patients Randomized Set [RND]

The all patients randomized (RND) set will contain all patients in the ENR set who are randomized to study treatment. For analyses and displays based on the RND set, patients will be classified according to randomized treatment.

5.3. Full Analysis Set [FAS]

The full analysis set (FAS) will contain all patients in the RND set who have collected sufficient data after intake of study treatment to compute any of the FEV₁ parameters (including peak FEV₁, trough FEV₁, AUC_{0-12h} FEV₁ and AUC_{0-3h} FEV₁) on at least one occasion. Patients will be classified according to randomized treatment.

5.4. Per-Protocol Set [PPS]

The per-protocol set (PPS) will contain all patients in the FAS set who had no major protocol deviations considered to influence the treatment effect of RPL554. Protocol deviations will be agreed and documented prior to database lock and unblinding. Patients will be classified according to randomized treatment.

5.5. Safety Analysis Set [SAF]

The safety analysis set (SAF) will contain all patients in the RND set who received at least one dose of study treatment. Patients will be classified according to actual treatment received.

5.6. PK data Set [PKS]

The pharmacokinetic (PK) data set (PKS) will contain all patients in the RND set who have blood sampling performed and a quantitative value of tiotropium and/ or RPL554 concentration determined. Patients will be classified according to actual treatment.

6. GENERAL CONSIDERATIONS

6.1. Reference Start Date and Period Day

The reference start date is defined as the day of the first dose of study treatment (RPL554 or placebo) and will appear in every listing where an assessment date or event date appears.

If the date of the event is on or after the reference start date, then:

Study Day = (date of event – reference start date) + 1.

If the date of the event is prior to the reference start date, then:

Study Day = (date of event – reference start date).

In the situation where the event date is partial or missing, Study Day and any corresponding durations will appear partial or missing in the listings, unless otherwise stated.

Document: ...\\Verona_Pharma\\RPL554\\BZA48916\\Biostatistics\\Documentation\\SAP\\Verona CO-205 SAP v1.0

Author: [REDACTED] Version Number: V1.0

Version Date: 05DEC2019

Template No.: CS_TP_BS016 Revision 5

Reference: CS_WI_BS005

Effective Date: 01Apr2018

6.2. Baseline

Unless otherwise specified, baseline is defined as the last non-missing measurement taken prior to study treatment start date (including unscheduled assessments). In the case where the last non-missing measurement and the study treatment start date coincide, the measurement will be considered pre-baseline, unless time is present. If time of the assessment is on or after the study treatment start date, then the assessment is not considered baseline. AEs and medications commencing on the reference start date will be considered post-baseline.

6.3. Retests and Unscheduled Visits

Retests, reschedules and unscheduled visits are permitted at the discretion of the Investigator.

All the data available, including unscheduled or unplanned readings will be presented within the patient listings, however only scheduled readings will be used in the summaries.

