Safety data including laboratory safety tests, 12-lead ECG, vital signs and physical examinations, will be summarized by treatment group and time point of collection, when appropriate, for each of the two parts separately. For continuous variables, the change from baseline (pre-dose at Visit 2) to each post-dose time point will also be calculated and summarized. Data will further be illustrated by shift tables (showing changes from low/normal/high) and shift plots for selected time points. Separate listings will be generated of abnormal values occurring after the first dose of study treatment.

Coded adverse event terms will be presented by system organ class (SOC) and preferred term and summarized by treatment group for each part. Summary tables by treatment group with total number and number of patients with adverse events, SAEs, adverse events leading to discontinuation of study treatment, causally related adverse events and severe adverse events will be produced. Further SAEs, causally related adverse events and adverse events of each intensity will be summarized by SOC and preferred term.

9.4.8 *Handling of Withdrawals or Missing Data*

Imputation of data for calculation of average (AUC) effects for FEV₁ and FVC will be described in the statistical analysis plan. No other imputation of missing data will be performed for the parameter computations. For the sensitivity ANCOVA analyses, missing data will be imputed using the last observation carried forward method prior to analysis.

All available data from all dosed patients who have received study treatment will be listed and summarized. Any unscheduled or unplanned readings will be presented within the patient listings, but only the scheduled readings will be used in any summaries.

9.4.9 *Interim Analyses*

No formal, unblinded interim analysis is planned for the study. To assess the plausibility of the assumptions in the sample size calculation, an estimate of the standard deviation of peak and AUC_{0-3h} FEV₁ will be made based on blinded data after completion of 125 patients. If the estimated standard deviations are markedly higher than the 200 mL assumed (>20%), a revised sample size estimation using the new standard and the previously used detectable difference (89) will be made. If the outcome is an increase of the sample size, an amendment will be submitted for approval.

9.5 *Determination of Sample Size*

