8. OUTPUT PRESENTATIONS

Appendix 1 shows conventions for presentation of data in outputs.

The shells document provided with this SAP describes the presentations for this study and therefore the format and content of the summary tables, figures, and listings to be provided by IQVIA Biostatistics.

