17.2. Laboratory Evaluations

Results from the central laboratory will be included in the reporting of this study for Hematology, Blood Chemistry, Urinalysis and Viral Serology. Measurements and timepoints for each laboratory assessment can be found in Table 3.

Presentations will use standard international (SI) Units.

The handling of re-tests and unscheduled measurements is detailed in Section 6.3.

Document: ...\\Verona_Pharma\\RPL554\\BZA48916\\Biostatistics\\Documentation\\SAP\\Verona CO-205 SAP v1.0

Author: [REDACTED] Version Number: V1.0

Version Date: 05DEC2019

Template No.: CS_TP_BS016 Revision 5

Reference: CS_WI_BS005

Effective Date: 01Apr2018

Table 3: Laboratory Assessments

Laboratory Assessment	Measurements	Time points
Hematology	hemoglobin, hematocrit, total white cell count, leukocyte differential count and platelet count	Screening and at the End of Study visit
Blood Chemistry	creatinine, total bilirubin, alkaline phosphatase, aspartate aminotransferase, alanine transaminase, gamma-glutamyl transferase, lactate dehydrogenase, creatine kinase, thyroid stimulating hormone*, triiodothyronine and thyroxine*, glucose, potassium, sodium and calcium	Screening and at the End of Study visit
Urinalysis	leukocytes, blood, ketones, bilirubin, urobilinogen, protein and glucose	Screening and at the End of Study visit
Viral Serology	human immunodeficiency virus, hepatitis B and hepatitis C serology	Screening

*Will only be measured at Screening.

The following summaries will be provided for laboratory data (Hematology, Blood Chemistry and Urinalysis), summarised by treatment group:

- Shift tables representing changes from Low/Normal/High, determined by reference normal range.
- Listings of patients meeting markedly abnormal criteria after the first dose

Change from baseline table by post-dose time-point of collection for continuous variables will be summarised by treatment group for Hematology and Blood Chemistry.

Viral Serology data will be listed.

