17.2.1. Laboratory Markedly Abnormal Criteria

Markedly abnormal quantitative safety (and other) laboratory assessments will be identified in accordance with the predefined markedly abnormal criteria as presented in Table 4. All laboratory parameter results will be listed.

Table 4: Markedly abnormal ranges for clinical laboratory parameters

Parameter	Markedly Abnormally High Criteria
Alanine Amino Transferase (ALT)	>3 times Upper Limit of Normal Range
Alkaline Phosphatase	>3 times Upper Limit of Normal Range
Aspartate Amino Transferase (AST)	>3 times Upper Limit of Normal Range
Creatinine	>221 µmol/L
Gamma Glutamyl Transferase (GGT)	>3 times Upper Limit of Normal Range
Total Bilirubin	>3 times Upper Limit of Normal Range

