APPENDIX 1. PROGRAMMING CONVENTIONS FOR OUTPUTS

Dates & Times

Depending on data available, dates and times will take the form yyyy-mm-ddThh:mm:ss.

Spelling Format

English US.

Presentation of Treatment Groups

For outputs, treatment groups will be represented as follows and in that order:

Treatment Group	For Tables, Listings and Figures
RPL554 0.375 mg	RPL554 0.375 mg
RPL554 0.75 mg	RPL554 0.75 mg
RPL554 1.5 mg	RPL554 1.5 mg
RPL554 3 mg	RPL554 3 mg
Placebo	Placebo

Decimal Places

The decimal places for this study will use the following rules, unless otherwise stated.

Value = x dp

Mean = x+1 dp

Standard Deviation = x+2 dp

Median = x+1 dp

Q1/Q3 = x+1 dp

Minimum/Maximum = x dp

CI = x+1 dp

For spirometry data we will present outputs with decimal places for value as follows:

- Values in litres = 3dp
- Values in millilitres = 0dp
- Percentage values = 1dp

P-values will be presented to 4dp.

Document: ...\\Verona_Pharma\\RPL554\\BZA48916\\Biostatistics\\Documentation\\SAP\\Verona CO-205 SAP v1.0

Author: [REDACTED] Version Number: V1.0

Version Date: 05DEC2019

Template No.: CS_TP_BS016 Revision 5

Reference: CS_WI_BS005

Effective Date: 01Apr2018

Presentation of Visits

For outputs, visits will be represented as follows and in that order, unless otherwise specified:

Long Name (default)	Short Name
Pre-Screening	Pre-Screening
Screening	Screening
Baseline	Baseline
Day 1	Day 1
Week 1	Week 1
Week 2	Week 2
Week 3	Week 3
Week 4	Week 4
Follow-up	FUP

Listings

All listings will be ordered by the following (unless otherwise indicated in the template):

- Randomized treatment group (or treatment received if it's a safety output)
- Centre-patient ID,
- Treatment day (where applicable),
- Date and time (if applicable),
- For listings where non-randomized patients are included, these will appear in a category after the randomized treatment groups labelled 'Not Randomized'.

Tables

All tables presenting multiple events that map to a SOC and PT will be counted only once, per unique patient, for incidence counts. Events will be presented in descending frequency of SOC and PT (unless otherwise indicated in the template).

Document: ...\\Verona_Pharma\\RPL554\\BZA48916\\Biostatistics\\Documentation\\SAP\\Verona CO-205 SAP v1.0

Author: [REDACTED] Version Number: V1.0

Version Date: 05DEC2019

Template No.: CS_TP_BS016 Revision 5

Reference: CS_WI_BS005

Effective Date: 01Apr2018

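### A markedly abnormal laboratory value found at an unscheduled test and resolved by Visit 6 is absent from both by-arm laboratory tables described in SAP 17.2

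*SAP*

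**What the plan says.** - SAP 6.3 leaves retests and unscheduled visits to the investigator's discretion. All such readings are listed, "however only scheduled readings will be used in the summaries". Protocol 9.4.8 has the same rule: "but only the scheduled readings will be used in any summaries".
- SAP 17.2 applies the rule to laboratory data: "The handling of re-tests and unscheduled measurements is detailed in Section 6.3".
- SAP Table 3 sets hematology, blood chemistry and urinalysis at "Screening and at the End of Study visit". Protocol 6.6.1 places the Visit 6 sample before dosing. The blood sample at Visit 4 (Protocol 6.5.1) is for pharmacokinetics only.
- SAP 17.2 plans two by-arm laboratory tables: a low/normal/high shift table, and a change-from-baseline table for hematology and chemistry. In the same block as the shift table it plans "Listings of patients meeting markedly abnormal criteria after the first dose". The thresholds are in SAP Table 4 (six analytes, high side only).
- SAP 17.2.1 lists all laboratory results, and Protocol 9.4.7 adds separate listings of abnormal values after first dose. SAP Appendix 1 sorts safety listings by treatment received.
- Protocol 7.4.3 allows unscheduled and repeat laboratory tests and merges their results into the final database.

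**The concern.** With one scheduled sample at the end of four weeks, both by-arm tables classify a completer by the Visit 6 value alone. Suppose a completer has ALT above 3 times the upper limit at an unscheduled test in Week 2 and a normal value at Visit 6. The shift table shows that patient as normal. The Week 2 value stands in a listing, where a reader has to count it by hand and supply the denominator.

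Protocol 1.1 says the study is meant to support dose selection for Phase III, and safety is a secondary objective. What is at stake is how easily four doses can be compared with placebo on markedly abnormal laboratory values. The primary endpoint is not involved.

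**Working it through.** The plan gives no figure on this point to reproduce. The check traces an unscheduled post-dose value through the outputs and then sizes the effect under stated assumptions.

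**Step 1. Scheduled samples after first dose, per completer.** Visit 6 pre-dose = 1. Patients who stop early have the End of Study visit as their scheduled sample, so the point is limited to completers.

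**Step 2. Where an unscheduled post-dose value can appear.**

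| Output | Admits the value? |
|---|---|
| Shift table by arm (SAP 17.2) | No, under SAP 6.3 |
| Change-from-baseline table by arm (SAP 17.2) | No, under SAP 6.3 |
| Listing of markedly abnormal patients (SAP 17.2) | Yes, if a Table 4 threshold is met; no count or denominator described |
| Full laboratory listing (SAP 17.2.1) and abnormal-value listing (Protocol 9.4.7) | Yes |
| Adverse-event tables by arm (SAP 17.1) | Only if reported as an adverse event |

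Visit windowing does not change this. SAP 6.4 windows only questionnaire, spirometry and rescue-medication data, and only for discontinued patients. SAP 6.2 lets an unscheduled pre-dose value serve as baseline, but that does not admit post-dose values.

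**Step 3. Size.** Inputs that the documents do not give are assumptions:
- onset uniform over the 28 treatment days;
- episode duration d days;
- probability q that an unscheduled test falls inside an episode that resolves before Visit 6;
- proportion r of patients with an episode.

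The 80 patients per arm come from Protocol 9.5.

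Share of episodes resolved before Visit 6 = 1 − d/28. For d = 3, 7 and 14 this is 25/28 = 89%, 21/28 = 75% and 14/28 = 50%. These shares reflect the sparse schedule. The reporting rule matters only for episodes that an unscheduled test detects, so its effect is (1 − d/28) × q:

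| d (days) | q = 10% | q = 25% | q = 50% |
|---|---|---|---|
| 3 | 8.9% | 22.3% | 44.6% |
| 7 | 7.5% | 18.8% | 37.5% |
| 14 | 5.0% | 12.5% | 25.0% |

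Patients per arm kept out of the tables = 80 × r × (1 − d/28) × q. For d = 7:
- r = 2%: 80 × 0.02 × 0.75 × q = 1.2q, which gives 0.12, 0.30 and 0.60;
- r = 5%: 80 × 0.05 × 0.75 × q = 3q, which gives 0.30, 0.75 and 1.50.

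Five of the six results are below one patient. One patient is 1/80 = 1.25% of an arm. Episodes that also reach the adverse-event tables are not subtracted.

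**Step 4. Other safety data.** ECG has 5 scheduled readings after first dose (Visit 2: 1; Visits 3 and 6: 2 each), with none between Weeks 1 and 4. Vital signs have 30 (Visit 2: 7; Visits 3 to 5: 5 each; Visit 6: 8). The same rule therefore costs less for ECG and little for vital signs.

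**The case against.** The strongest reply is that nothing here is wrong. Protocol and SAP agree, safety is descriptive, and the information is reported already. SAP 17.2 says of the analytes in Table 4: "Listings of patients meeting markedly abnormal criteria after the first dose". That item is not tied to scheduled visits, sits among the outputs to be given by treatment group, and is sorted by treatment. Abnormalities reported as adverse events are tabulated by arm. The scheduled-only rule also has a sound reason: retesting is discretionary, so a worst-value table measures how often patients were tested as well as what the drug did. Finally, the format and content of the tables are in a separate file ("The shells document provided with this SAP describes the presentations for this study"), which is not among the documents, so a by-arm count may already be planned.

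Most of this stands. A reader might infer that unscheduled results are excluded from every summary, or that a safety signal would be lost. The documents support neither. The listing of markedly abnormal patients is itself grouped with the summaries in SAP 17.2, and the values remain in the full listings. A reader might also take 89%, 75% and 50% as the effect of the rule. They are upper bounds, reached only if q = 100%.

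Two things remain. A listing gives no count or denominator. The adverse-event route depends on reporting: Protocol 7.4.3 has the investigator judge clinical significance, but Protocol 7.4.1 states no rule that a significant laboratory value must be recorded as an adverse event. The retesting objection weighs most against a worst-value shift table. A count on fixed Table 4 thresholds is less exposed, though not free of it.

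**Conclusion.** The point holds in limited form. Under the stated rule, neither by-arm laboratory table described in SAP 17.2 can show a markedly abnormal value that was found off schedule and had resolved by Visit 6. The textual part needs no assumption beyond the SAP text; the output shells could not be checked. For 7-day episodes the expected number kept out is 0.12 to 1.50 patients per arm of 80, and incidence, duration and the chance of an unscheduled test are all assumed. No primary conclusion changes. This is a cheap improvement to reporting and not an error in the plan.

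**What to change.** Keep the scheduled-only tables as they are. Amend SAP 6.3 and 17.2 to add one by-arm table: the number and percentage of patients with any value after first dose that meets SAP Table 4 criteria, with unscheduled and repeat readings included. Footnote the number of unscheduled laboratory tests per arm. Record the change in SAP 3.3 and report it in the study report as a departure from Protocol 9.4.8, as Protocol 9.1 provides. No protocol amendment is needed. If the output shells already contain such a count, only the SAP wording has to be aligned.

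The cost is a few sentences and one table, with no new data collection. The downside is that discretionary retesting may raise counts unevenly across arms; the footnote discloses this but does not remove it. The table also covers only the six analytes in Table 4, so an off-schedule abnormal potassium, glucose or hematology value would still appear only in listings. A worst-post-baseline shift table, and similar additions for ECG and vital signs, are optional.
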